4. TRIAL DESIGN

Dukes C colon cancer, high risk Dukes B colon cancer, Dukes B rectal cancer or Dukes C rectal cancer patients who have completed the resection of primary tumour will be treated with standard

therapy (chemotherapy ± radiotherapy). Adjuvant chemotherapy is not specified but should consist of at least 3 months of a 5FU based chemotherapy – for example, weekly 5FU/FA (Roswell Park regimen), monthly 5FU/FA (Mayo Clinic regimen), infusion of 5FU, oral capecitabine, FOLFOX or Capecitabine/Oxaliplatin regimens. Rectal cancers may additionally have adjuvant radiotherapy administered in either adjuvant or neoadjuvant fashion. During the last cycle of standard therapy, prospective patients would be invited to participate in this study. Once informed consent is taken & within 120 days of completion of the standard therapy, they would be checked for trial eligibility.

An eligible subject will be randomised to the study in 1:1 ratio to either

- Aspirin arm: 200 mg Aspirin once a day for 3 years
- Placebo arm: 200 mg matching placebo once a day for 3 years.

After randomisation, patient will have 3 monthly assessments for 3 years (month 3 to month 36) followed by 6 monthly assessments for additional 2 years (month 42 to month 60). All subjects will be approached to seek consent for survival information (DFS, OS) after 5 years post randomization will have data collected via review of medical records or by phone contact, every 12 months until, and at the last patient last visit (month 60 visit or earlier) at the site.

The purpose of 5 year follow up is to evaluate-

1. The long term survival outcomes and
2. Persistence of effect after completion of treatment.

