7.8. Anticipated side effects of Aspirin

Side effects that occasionally occur are gastrointestinal disorders such as nausea, vomiting, diarrhoea, and slight gastrointestinal blood loss which in exceptional cases can lead to anaemia. Gastrointestinal ulcers may rarely develop, in some circumstances with haemorrhaging and

perforation. Dizziness and ringing in the ear can occur as symptoms of over dosage, especially in children and elderly patients.

Rare cases of hypersensitivity reactions (e.g. difficulty in breathing, skin reaction) can occur.

Isolated cases of liver and kidney function disturbances, and severe skin reactions have been reported.

The absolute annual increase risk attributable to Aspirin for major bleeding, major gastrointestinal bleeding and intracranial haemorrhage is estimated at 0.13%, 0.12% and 0.03% respectively. (McQuaid KR et al)

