3.1 Randomisation

Randomisation will occur within 120 days of completion of standard therapy. After informed consent is signed and subject's eligibility is confirmed, the subject can be randomised in a 1:1

allocation ratio (Aspirin group: 200 mg Aspirin once a day for 3 years or placebo group: 200 mg matching placebo once a day for 3 years), stratified by

- Study centre
- Tumour type (Dukes C colon, high risk Dukes B colon cancer, or rectal cancer sub-groups) and
- Type of adjuvant chemotherapy received (exposed/ not exposed to Oxaliplatin)

All randomisations will be done via direct web randomisation. Authorised study centre personnel will randomise the subjects via a password-protected internet web site provided by Singapore Clinical Research Institute.

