3.2 Treatment Schedule

A total of 1587 subjects will be randomised from multinational centres. After randomisation, subject will have 3-monthly assessments for 3 years (month 3 to month 36) followed by 6-monthly assessments for additional 2 years (month 42 to month 60). Subjects who consent to continue information collection after month 60 will have vital data captured via review of medical records or phone call.

The study drug, oral Aspirin 200 mg/ placebo 200 mg once a day, should begin immediately but no later than 2 weeks of randomisation. The study drug will be stopped immediately if there is a disease recurrence confirmed by CT, histology or cytology. In the event of SAE related to the study drug, the study drug will be stopped immediately.

The investigator has the right to discontinue study treatment if he/she feels that it is in the best interests of the subject or due to safety concerns. The reasons for treatment discontinuation will be documented. All subjects, including subjects who discontinued from study treatment, will continue to be followed for 5 years after randomisation, unless the subject is lost to follow up, died or withdrew consent.

3.3

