4.7 Safety Endpoints

The evaluation of drug safety is based on clinical adverse events and laboratory abnormalities reported during the study. All safety presentations will be based on actually-treated subject dataset.

AEs and SAEs will be summarised using the following method:

Number and percentage of subjects who ever reported adverse event (AE) and serious adverse event (SAE) together with the number of AEs and SAEs will be presented by treatment group. The severity and outcome of AEs and SAEs, relationship to treatment and action taken will be summarised.

Same AE term reported at multiple level of severities by a single subject will be counted for each level of severity, not just the highest severity. Under subject counts at each severity category, only unique subject will be counted. The same method will also be applied for summaries by relationship, treatment given, outcome, and action taken.

All on-study adverse events will be further summarised by MedDRA terminology. Summaries of AEs will be based on the resulting system organ class (SOC) and preferred terms (PT). All reported SAEs will be listed indicating the subject ID, SAE criteria, randomisation date, onset date, resolution date, relationship to study treatment and outcome of causality.

The term “AEs” used in the summaries would cover severe AEs and SAEs as well.

Number of subjects who ever experienced the following medical events including acute myocardial infarct, ischaemic stroke, new cancer (non-colorectal), major GI bleeding (requiring blood transfusion), haemorrhagic stroke and major nervous system bleeding throughout the study will be counted and its corresponding percentages will be respectively compared between the two treatment groups using Fisher’s exact test.

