Preferred term X	xx (xx.x)	xx	xx (xx.x)	xx	xx	xx (xx.x)	xx	xx	xx (xx.x)	xx	xx	xx (xx.x)

Placebo
(N = xxx)

System Organ Class Preferred Term	MILD			MODERATE			SEVERE			UNKNOWN		
	n (%)	nAE	n (%)	n (%)	nAE	n (%)	n (%)	nAE	n (%)	n (%)	nAE	n (%)
System organ class 1	xx (xx.x)	xx	xx (xx.x)	xx	xx	xx (xx.x)	xx	xx	xx (xx.x)	xx	xx	xx (xx.x)
Preferred term 1	xx (xx.x)	xx	xx (xx.x)	xx	xx	xx (xx.x)	xx	xx	xx (xx.x)	xx	xx	xx (xx.x)

Preferred term 2	XX (XX.X)	XX	XX (XX.X)	XX	XX (XX.X)	XX	XX (XX.X)	XX
Preferred term 3	XX (XX.X)	XX	XX (XX.X)	XX	XX (XX.X)	XX	XX (XX.X)	XX
...	XX (XX.X)	XX	XX (XX.X)	XX	XX (XX.X)	XX	XX (XX.X)	XX
System organ class X	XX (XX.X)	XX	XX (XX.X)	XX	XX (XX.X)	XX	XX (XX.X)	XX
Preferred term X	XX (XX.X)	XX	XX (XX.X)	XX	XX (XX.X)	XX	XX (XX.X)	XX

n (%) = number (percent) of subjects.

nAE = number of adverse events.

Table 12: Serious adverse events by system organ class

System Organ Class Preferred Term	Aspirin (N = xxx)		Placebo (N = xxx)	
	n (%)	nAE	n (%)	nAE
System organ class 1	xx (xx.x)	xx	xx (xx.x)	xx
Preferred term 1	xx (xx.x)	xx	xx (xx.x)	xx
Preferred term 2	xx (xx.x)	xx	xx (xx.x)	xx
Preferred term 3	xx (xx.x)	xx	xx (xx.x)	xx
...				
...				
System organ class X	xx (xx.x)	xx	xx (xx.x)	xx
Preferred term X	xx (xx.x)	xx	xx (xx.x)	xx

n (%) = number (percent) of subjects.

nAE = number of adverse events.

Table 13: Severe adverse events related to treatment by system organ class

System Organ Class Preferred Term	Population: Safety population			
	Aspirin (N = xxx)		Placebo (N = xxx)	
	n (%)	nAE	n (%)	nAE
System organ class 1	xx (xx.x)	xx	xx (xx.x)	xx
Preferred term 1	xx (xx.x)	xx	xx (xx.x)	xx
Preferred term 2	xx (xx.x)	xx	xx (xx.x)	xx
Preferred term 3	xx (xx.x)	xx	xx (xx.x)	xx
...				
...				
System organ class X	xx (xx.x)	xx	xx (xx.x)	xx
Preferred term X	xx (xx.x)	xx	xx (xx.x)	xx

Related adverse events are defined as those with “Unknown”, “Possible”, “Probable”, “Definite” relationship with study treatment.

n (%) = number (percent) of subjects.

nAE = number of adverse events.

Table 14: Medical events
Population: Safety population

n (%)	Aspirin (N=xxxx)	Placebo (N=xxxx)	P-value ¹
Acute myocardial infarct			0.xxx
Yes	xx (xx.x)	xx (xx.x)	
No	xx (xx.x)	xx (xx.x)	
Ischaemic stroke			0.xxx
Yes	xx (xx.x)	xx (xx.x)	
No	xx (xx.x)	xx (xx.x)	
New cancer (non-colorectal)			0.xxx
Yes	xx (xx.x)	xx (xx.x)	
No	xx (xx.x)	xx (xx.x)	
Major GI bleeding			0.xxx
Yes	xx (xx.x)	xx (xx.x)	
No	xx (xx.x)	xx (xx.x)	
Hemorrhagic stroke			0.xxx

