Yes	xx (xx.x)	xx (xx.x)	
No	xx (xx.x)	xx (xx.x)	
Major nervous system bleeding			0.xxx
Yes	xx (xx.x)	xx (xx.x)	
No	xx (xx.x)	xx (xx.x)	

n: number of subjects; %: percentage of randomised in each treatment group; GI: gastrointestinal bleeding.
¹Fisher's exact test.

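### The only formal between-arm safety comparison is a Fisher p-value per medical event with no risk difference or interval, and it has at most about 9% power for the bleeding excess the protocol expects

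*SAP*

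**What the plan says.** SAP 4.7 presents adverse events and serious adverse events by arm as counts and percentages, without tests. The one formal comparison is for six medical events: acute myocardial infarct, ischaemic stroke, new non-colorectal cancer, major GI bleeding requiring transfusion, haemorrhagic stroke and major nervous system bleeding. For these, the "corresponding percentages will be respectively compared between the two treatment groups using" Fisher's exact test. The mock-up, "Table 14: Medical events" in SAP Appendix 1, has n (%) for Yes and No in each arm and a p-value column. It has no effect estimate and no interval. SAP 4.1 makes tests two-sided, calls p<0.05 significant, and sets 95% as the level of any interval, but does not require an interval for safety.

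Protocol 7.8 gives the expected harm: the annual excess with aspirin for "major bleeding, major gastrointestinal bleeding and intracranial haemorrhage is estimated at 0.13%, 0.12% and 0.03% respectively".

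For efficacy, SAP Table 7 does plan absolute differences in DFS and OS rates at 3 and 5 years, each with a 95% interval.

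On the denominator, SAP 4.7 bases all safety output on patients as actually treated, and Table 14 is headed as the safety population. Its footnote, however, defines the percentage as "percentage of randomised in each treatment group".

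**The concern.** The protocol expects a bleeding excess that is small in absolute terms. With so few events, a significance test separates poorly between no excess and the expected excess, and a bare p-value does not show how large an excess remains compatible with the data. That range is what a reader needs when weighing a long-term preventive treatment. As planned, absolute benefit would have an interval and absolute bleeding harm would not, so the two could not be read on the same scale.

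**Working it through.** **Inputs from the documents**
- Size: "A total of 1587 subjects will be randomised from multinational centres" (SAP 3.2), with 1:1 allocation (SAP 3.1), so 794 and 793 patients.
- Duration: "Aspirin arm: 200 mg Aspirin once a day for 3 years" (Protocol 4).
- Annual excess: 0.12% for major GI bleeding and 0.03% for intracranial haemorrhage (Protocol 7.8).
- Test: Fisher's exact, two-sided, p<0.05 (SAP 4.7 and 4.1).

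**Assumptions**
- The placebo risk is not in the documents, so it is varied from 0 to 1% over 3 years.
- The annual excess applies for the 3 treatment years and no longer.

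**The plan's own figure.** The sample size comes from DFS: 300 / (1 − 0.79) / (1 − 0.10) = 1587.3, which matches 1587. The documents state no power or precision for any safety endpoint.

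**Expected excess in the aspirin arm**
- Major GI bleeding: 0.12% × 3 = 0.36%; 794 × 0.0036 = 2.9 patients.
- Intracranial haemorrhage: 0.03% × 3 = 0.09%; 794 × 0.0009 = 0.7 patients.

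**Exact Fisher power.** Sum P(a)·P(b) over all pairs of counts (a, b) with two-sided Fisher p<0.05, where a is binomial(794, placebo risk + excess) and b is binomial(793, placebo risk).

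| Assumed 3-year placebo risk | Major GI bleeding, excess 0.36% | Intracranial haemorrhage, excess 0.09% |
|---|---|---|
| 0 | 7.0% | <0.1% |
| 0.125% | 8.8% | 0.4% |
| 0.25% | 8.9% | 1.4% |
| 0.5% | 7.9% | 2.8% |
| 1% | 6.6% | 3.6% |

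The maximum for major GI bleeding is 9.0%, at a placebo risk of about 0.2%. If the true excess is the one in Protocol 7.8, the result is non-significant at least 91% of the time.

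**Sensitivity for major GI bleeding**
- Removing the planned 10% attrition (714 per arm) gives 4.7 to 7.2%.
- Counting 5 years of background bleeding with a 3-year excess gives 5 to 9%.
- If the excess itself ran for 5 years, power would be about 8 to 34%, but study drug stops at 3 years.
- The 0.13% per year excess for all major bleeding would give at most 10.8%, but the SAP does not test that composite.

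**Counts needed for significance.** 6 vs 0 (p=0.031), 8 vs 1, 10 vs 2 or 13 vs 4. By contrast, 5 vs 0 (p=0.062), 7 vs 1 (p=0.070) and 12 vs 4 (p=0.075) are all non-significant. At a placebo risk of 0.5%, a 4-fold risk gives 73% power and a 4.5-fold risk gives 83%.

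**What an interval adds (illustrative counts, 7 vs 4).** Fisher p=0.55.
- Risks: 7/794 = 0.882% and 4/793 = 0.504%; difference +0.377%.
- Wilson limits: 0.428% to 1.809% (aspirin) and 0.196% to 1.290% (placebo).
- Newcombe lower limit: 0.377 − √[(0.882 − 0.428)² + (1.290 − 0.504)²] = −0.53%.
- Newcombe upper limit: 0.377 + √[(1.809 − 0.882)² + (0.504 − 0.196)²] = +1.35%.

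The interval contains zero, the expected +0.36%, and values up to 1.35 / 0.36 = 3.75 times that. The p-value alone shows none of this.

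**The case against.** Low power is not a fault of Fisher's test. The trial was sized for DFS, SAP section 2 lists no safety objective, and the plan never claims to detect a bleeding excess. About 80% power for the expected GI excess would need roughly 4,300 to 10,800 patients per arm at placebo rates of 0.06 to 0.24% per year, so no choice of analysis could supply it. That stands: a reader might infer a design failure, and the documents do not support one. The low power is instead the reason a p-value is a poor summary here.

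Table 14 gives counts and denominators, so any reader could derive the interval. That is true, but it does not make a p-value an adequate planned comparison, and the SAP does not leave readers to derive the differences in DFS and OS rates.

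Adverse events and serious adverse events are also set out by arm in Tables 9 to 13, and serious events are listed individually. That stands: Fisher's test is the only formal comparison, not the only view of safety by arm.

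The figures rest on an assumed placebo risk and on matching Protocol 7.8 to the SAP events. The SAP restricts GI bleeding to cases needing transfusion and splits haemorrhagic stroke from other major nervous system bleeding. One decimal place therefore overstates the precision, but the size of the result is the same across the range tried.

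**Conclusion.** The point holds as an analysis and reporting weakness. It does not touch the primary result. If the true excess is the one in Protocol 7.8, acting over 3 years in 794 vs 793 patients, Fisher power is at most about 9% for major GI bleeding and about 4% or less for intracranial haemorrhage, at assumed 3-year placebo risks of 0 to 1%. A non-significant p-value would be the usual outcome whether or not that excess exists. A much larger excess, of 4- to 5-fold at a placebo risk of 0.5%, could still be detected.

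Two stronger readings go beyond the documents. One is that the trial will be reported as showing no bleeding harm. The SAP says only when a result is called significant, and nowhere treats non-significance as absence of harm. The other is that Table 14 mixes numerators and denominators from different sets of patients. SAP 4.7 and the table heading both name the as-treated safety population, so the footnote is a wording conflict with the governing text.

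**What to change.** In SAP 4.7 and Table 14, make the risk difference (aspirin minus placebo) with a 95% Newcombe or score interval the main comparison for each of the six events. Keep Fisher's p-value as secondary, and state that a non-significant value is not evidence of no excess. Reword the Table 14 footnote so that percentages are of the safety population as treated.

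The cost is one table column, a sentence or two in SAP 4.7 and one footnote. No new data are needed, and the primary analysis, alpha and sample size do not change.

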4.8 Interim Analysis

Interim analyses were scheduled every year as long as there is subject still on study treatment. An independent Data Monitoring Committee (DMC) was established to review the interim results of the study. Ideally, the first interim analysis should be done after 540 subjects have been recruited or at the midpoint (end of Year 2012) of the targeted recruitment period, whichever comes earlier. The second interim analysis should be done once 540 subjects have

been followed up for 3 years (approximately between fifth to sixth years). Treatment allocations in all the interim analyses were masked with the label “Group A” and “Group B”.

Safety was the main aspect for review in the first DMC meeting. A report containing non-confidential data was sent to the Study Steering Committee. Randomisation, compliance, CRF received and processed, AE and SAE were included in this DMC report. The study endpoints reviewed in the second interim analysis were DFS and OS, as well as safety profiles. Subsequent reviews of DFS and OS were done upon request of DMC.

The analysis results of the interim analyses were not the sole criteria for deciding whether to early terminate the study. Rather they provided a guideline to aid in the decision, which also took into account the characteristics of the subjects, nature of toxicities, relevant external results. Another goal of this monitoring was to review the number of events needed for the primary analysis and whether the sample size needed to be adjusted to achieve the targeted number of events.

4.9 Final Analysis

Final analysis will be performed after pre-determined number of recurrences (or deaths) has been observed (i.e. 300 recurrences or death) and all subjects have completed a minimum follow-up of 1 year. The date for last patient last visit is 31 March 2023.

APPENDICES

Appendix 1: Mock-up tables

Table 1: Subject status and demographics

	Modified intention-to-treat			Per-protocol		
	Aspirin	Placebo	Total	Aspirin	Placebo	Total
Number of subjects randomised	xxx	xxx	xxx	xxx	xxx	xxx
Number of subjects ineligible but randomised, n (%)	xx (xx.x)	xx (xx.x)	xx (xx.x)	xx (xx.x)	xx (xx.x)	xx (xx.x)
Subjects discontinued study treatment, n (%)	xx (xx.x)	xx (xx.x)	xx (xx.x)	xx (xx.x)	xx (xx.x)	xx (xx.x)
Completed protocol treatment	xx (xx.x)	xx (xx.x)	xx (xx.x)	xx (xx.x)	xx (xx.x)	xx (xx.x)
AE/SAE	xx (xx.x)	xx (xx.x)	xx (xx.x)	xx (xx.x)	xx (xx.x)	xx (xx.x)
Protocol violation/ ineligibility	xx (xx.x)	xx (xx.x)	xx (xx.x)	xx (xx.x)	xx (xx.x)	xx (xx.x)
Clinical decision	xx (xx.x)	xx (xx.x)	xx (xx.x)	xx (xx.x)	xx (xx.x)	xx (xx.x)
Subject decision	xx (xx.x)	xx (xx.x)	xx (xx.x)	xx (xx.x)	xx (xx.x)	xx (xx.x)
Recurrence	xx (xx.x)	xx (xx.x)	xx (xx.x)	xx (xx.x)	xx (xx.x)	xx (xx.x)
Death	xx (xx.x)	xx (xx.x)	xx (xx.x)	xx (xx.x)	xx (xx.x)	xx (xx.x)
Others	xx (xx.x)	xx (xx.x)	xx (xx.x)	xx (xx.x)	xx (xx.x)	xx (xx.x)
Subjects who did not complete study, n (%)	xxx (xx.x)	xxx (xx.x)	xxx (xx.x)	xxx (xx.x)	xxx (xx.x)	xxx (xx.x)
Subject withdrew consent	xx (xx.x)	xx (xx.x)	xx (xx.x)	xx (xx.x)	xx (xx.x)	xx (xx.x)
Withdrawn from study by investigator	xx (xx.x)	xx (xx.x)	xx (xx.x)	xx (xx.x)	xx (xx.x)	xx (xx.x)
Lost to follow-up	xx (xx.x)	xx (xx.x)	xx (xx.x)	xx (xx.x)	xx (xx.x)	xx (xx.x)
Death	xx (xx.x)	xx (xx.x)	xx (xx.x)	xx (xx.x)	xx (xx.x)	xx (xx.x)
Others	xx (xx.x)	xx (xx.x)	xx (xx.x)	xx (xx.x)	xx (xx.x)	xx (xx.x)

Subject follow-up completion, n (%)

1 year follow-up	XX (XX.X)	XX (XX.X)	XX (XX.X)	XX (XX.X)	XX (XX.X)	XX (XX.X)
2 year follow-up	XX (XX.X)	XX (XX.X)	XX (XX.X)	XX (XX.X)	XX (XX.X)	XX (XX.X)
3 year follow-up	XX (XX.X)	XX (XX.X)	XX (XX.X)	XX (XX.X)	XX (XX.X)	XX (XX.X)
4 year follow-up	XX (XX.X)	XX (XX.X)	XX (XX.X)	XX (XX.X)	XX (XX.X)	XX (XX.X)
5 year follow-up	XX (XX.X)	XX (XX.X)	XX (XX.X)	XX (XX.X)	XX (XX.X)	XX (XX.X)

Subject follow-up time, month

Mean (SD)	XX.X (XX.X)	XX.X (XX.X)	XX.X (XX.X)	XX.X (XX.X)	XX.X (XX.X)	XX.X (XX.X)
Median (IQR)	XX.X (XX.X)	XX.X (XX.X)	XX.X (XX.X)	XX.X (XX.X)	XX.X (XX.X)	XX.X (XX.X)
Min, Max	XX.X, XX.X	XX.X, XX.X	XX.X, XX.X	XX.X, XX.X	XX.X, XX.X	XX.X, XX.X

Demographics

Age, year

n	XXX	XXX	XXX	XXX	XXX	XXX
Mean (SD)	XX.X (XX.X)	XX.X (XX.X)	XX.X (XX.X)	XX.X (XX.X)	XX.X (XX.X)	XX.X (XX.X)
Median (IQR)	XX.X (XX.X)	XX.X (XX.X)	XX.X (XX.X)	XX.X (XX.X)	XX.X (XX.X)	XX.X (XX.X)
Min, Max	XX.X, XX.X	XX.X, XX.X	XX.X, XX.X	XX.X, XX.X	XX.X, XX.X	XX.X, XX.X

Age group, n (%)

<70	XXX (XX.X)	XXX (XX.X)	XXX (XX.X)	XXX (XX.X)	XXX (XX.X)	XXX (XX.X)
≥70	XXX (XX.X)	XXX (XX.X)	XXX (XX.X)	XXX (XX.X)	XXX (XX.X)	XXX (XX.X)

Gender, n (%)

Male	XXX (XX.X)	XXX (XX.X)	XXX (XX.X)	XXX (XX.X)	XXX (XX.X)	XXX (XX.X)
Female	XXX (XX.X)	XXX (XX.X)	XXX (XX.X)	XXX (XX.X)	XXX (XX.X)	XXX (XX.X)

Ethnicity, n (%)									
East Asian	xxx (xx.x)	xxx (xx.x)	xxx (xx.x)	xxx (xx.x)	xxx (xx.x)	xxx (xx.x)	xxx (xx.x)	xxx (xx.x)	xxx (xx.x)
South Asian	xxx (xx.x)	xxx (xx.x)	xxx (xx.x)	xxx (xx.x)	xxx (xx.x)	xxx (xx.x)	xxx (xx.x)	xxx (xx.x)	xxx (xx.x)
Caucasian	xxx (xx.x)	xxx (xx.x)	xxx (xx.x)	xxx (xx.x)	xxx (xx.x)	xxx (xx.x)	xxx (xx.x)	xxx (xx.x)	xxx (xx.x)
Others	xxx (xx.x)	xxx (xx.x)	xxx (xx.x)	xxx (xx.x)	xxx (xx.x)	xxx (xx.x)	xxx (xx.x)	xxx (xx.x)	xxx (xx.x)
Country, n (%)									
Country 1	xxx (xx.x)	xxx (xx.x)	xxx (xx.x)	xxx (xx.x)	xxx (xx.x)	xxx (xx.x)	xxx (xx.x)	xxx (xx.x)	xxx (xx.x)
Country 2	xxx (xx.x)	xxx (xx.x)	xxx (xx.x)	xxx (xx.x)	xxx (xx.x)	xxx (xx.x)	xxx (xx.x)	xxx (xx.x)	xxx (xx.x)
...	xxx (xx.x)	xxx (xx.x)	xxx (xx.x)	xxx (xx.x)	xxx (xx.x)	xxx (xx.x)	xxx (xx.x)	xxx (xx.x)	xxx (xx.x)
Country Y	xxx (xx.x)	xxx (xx.x)	xxx (xx.x)	xxx (xx.x)	xxx (xx.x)	xxx (xx.x)	xxx (xx.x)	xxx (xx.x)	xxx (xx.x)
Diet, n (%)									
Vegetarian (including egg)	xxx (xx.x)	xxx (xx.x)	xxx (xx.x)	xxx (xx.x)	xxx (xx.x)	xxx (xx.x)	xxx (xx.x)	xxx (xx.x)	xxx (xx.x)
Non-vegetarian	xxx (xx.x)	xxx (xx.x)	xxx (xx.x)	xxx (xx.x)	xxx (xx.x)	xxx (xx.x)	xxx (xx.x)	xxx (xx.x)	xxx (xx.x)

n: number of subjects; %: percentage of respective population pool treatment group; AE: adverse event; SAE: serious adverse event; SD: standard deviation; IQR: interquartile range.

Table 2: Study treatment exposure

	Modified intention-to-treat			Per-protocol	
	Aspirin	Placebo	Total	Aspirin	Placebo
Number of compliant subjects, n (%)	xx (xx.x)	xx (xx.x)	xx (xx.x)	xx (xx.x)	xx (xx.x)
Duration of exposure to study drug, n (%)					
<1 year	xx (xx.x)	xx (xx.x)	xx (xx.x)	xx (xx.x)	xx (xx.x)
1-2 years	xx (xx.x)	xx (xx.x)	xx (xx.x)	xx (xx.x)	xx (xx.x)
>2 years	xx (xx.x)	xx (xx.x)	xx (xx.x)	xx (xx.x)	xx (xx.x)
Duration of exposure to study drug, day					
N	xxx	xxx	xxx	xxx	xxx
Mean (SD)	xx.x (xx.x)	xx.x (xx.x)	xx.x (xx.x)	xx.x (xx.x)	xx.x (xx.x)
Median (IQR)	xx.x (xx.x)	xx.x (xx.x)	xx.x (xx.x)	xx.x (xx.x)	xx.x (xx.x)
Min, Max	xx.x, xx.x	xx.x, xx.x	xx.x, xx.x	xx.x, xx.x	xx.x, xx.x

Note: Compliant subject is defined as an individual who is on study drug for at least 70% of days in first year from randomisation or up to study discontinuation or recurrence, whichever is earlier. Duration of exposure is defined using the following formula: “duration of exposure” = “last dosing date” – “first dosing date” – “days off medication” + “1 day”.

n: number of subjects; %: percentage of respective population pool treatment group; AE: adverse event; SAE: serious adverse event; SD: standard deviation; IQR: interquartile range.

Table 3: Colorectal cancer status and adjuvant therapy received

	Modified intention-to-treat		Per-protocol
	Aspirin (N=xxxx)	Placebo (N=xxxx)	
Colorectal cancer status			
Time from surgery to randomisation, day			
n	xxx	xxx	xxx
Mean (SD)	xx.x (xx.x)	xx.x (xx.x)	xx.x (xx.x)
Median (IQR)	xx.x (xx.x)	xx.x (xx.x)	xx.x (xx.x)
Min, Max	xx.x, xx.x	xx.x, xx.x	xx.x, xx.x
Type of surgery, n (%)			
Laparoscopic surgery	xxx (xx.x)	xxx (xx.x)	xxx (xx.x)
Open surgery	xxx (xx.x)	xxx (xx.x)	xxx (xx.x)
Tumour location, n (%)			
Caecum	xxx (xx.x)	xxx (xx.x)	xxx (xx.x)
Ascending colon	xxx (xx.x)	xxx (xx.x)	xxx (xx.x)
Hepatic flexure	xxx (xx.x)	xxx (xx.x)	xxx (xx.x)
Transverse colon	xxx (xx.x)	xxx (xx.x)	xxx (xx.x)
Splenic flexure	xxx (xx.x)	xxx (xx.x)	xxx (xx.x)
Descending colon	xxx (xx.x)	xxx (xx.x)	xxx (xx.x)
Sigmoid colon/ rectosigmoid colon	xxx (xx.x)	xxx (xx.x)	xxx (xx.x)
Rectum	xxx (xx.x)	xxx (xx.x)	xxx (xx.x)
T-staging, n (%)			
T1	xxx (xx.x)	xxx (xx.x)	xxx (xx.x)

T2	XXX (XX.X)	XXX (XX.X)	XXX (XX.X)	XXX (XX.X)
T3	XXX (XX.X)	XXX (XX.X)	XXX (XX.X)	XXX (XX.X)
T4	XXX (XX.X)	XXX (XX.X)	XXX (XX.X)	XXX (XX.X)
Unknown	XXX (XX.X)	XXX (XX.X)	XXX (XX.X)	XXX (XX.X)
Tumour type, n (%)				
Dukes C colon cancer	XXX (XX.X)	XXX (XX.X)	XXX (XX.X)	XXX (XX.X)
High risk Dukes B colon cancer	XXX (XX.X)	XXX (XX.X)	XXX (XX.X)	XXX (XX.X)
Rectal cancer (Dukes B or Dukes C)	XXX (XX.X)	XXX (XX.X)	XXX (XX.X)	XXX (XX.X)
Proximal margin involved	XXX (XX.X)	XXX (XX.X)	XXX (XX.X)	XXX (XX.X)
Distal margin involved	XXX (XX.X)	XXX (XX.X)	XXX (XX.X)	XXX (XX.X)
Circumferential margin involved	XXX (XX.X)	XXX (XX.X)	XXX (XX.X)	XXX (XX.X)
Histology, n (%)				
Mucinous	XXX (XX.X)	XXX (XX.X)	XXX (XX.X)	XXX (XX.X)
Adenocarcinoma	XXX (XX.X)	XXX (XX.X)	XXX (XX.X)	XXX (XX.X)
Signet ring type	XXX (XX.X)	XXX (XX.X)	XXX (XX.X)	XXX (XX.X)
Others	XXX (XX.X)	XXX (XX.X)	XXX (XX.X)	XXX (XX.X)
Unknown	XXX (XX.X)	XXX (XX.X)	XXX (XX.X)	XXX (XX.X)
Any synchronous tumours, n (%)				
XXX (XX.X)	XXX (XX.X)	XXX (XX.X)	XXX (XX.X)	XXX (XX.X)
Adjuvant therapy received				
First chemo regimen, n (%)				
Capecitabine	XXX (XX.X)	XXX (XX.X)	XXX (XX.X)	XXX (XX.X)
5-fu bolus	XXX (XX.X)	XXX (XX.X)	XXX (XX.X)	XXX (XX.X)
Infusional 5-fu	XXX (XX.X)	XXX (XX.X)	XXX (XX.X)	XXX (XX.X)

Folfox	XXX (XX.X)	XXX (XX.X)	XXX (XX.X)	XXX (XX.X)	XXX (XX.X)
Capecitabine – oxaliplatin	XXX (XX.X)	XXX (XX.X)	XXX (XX.X)	XXX (XX.X)	XXX (XX.X)
Others	XXX (XX.X)	XXX (XX.X)	XXX (XX.X)	XXX (XX.X)	XXX (XX.X)
Cycle duration, weeks					
n	XXX	XXX	XXX	XXX	XXX
Mean (SD)	XX.X (XX.X)	XX.X (XX.X)	XX.X (XX.X)	XX.X (XX.X)	XX.X (XX.X)
Median (IQR)	XX.X (XX.X)	XX.X (XX.X)	XX.X (XX.X)	XX.X (XX.X)	XX.X (XX.X)
Min, Max	XX.X, XX.X	XX.X, XX.X	XX.X, XX.X	XX.X, XX.X	XX.X, XX.X
No. of cycles completed					
n	XXX	XXX	XXX	XXX	XXX
Mean (SD)	XX.X (XX.X)	XX.X (XX.X)	XX.X (XX.X)	XX.X (XX.X)	XX.X (XX.X)
Median (IQR)	XX.X (XX.X)	XX.X (XX.X)	XX.X (XX.X)	XX.X (XX.X)	XX.X (XX.X)
Min, Max	XX.X, XX.X	XX.X, XX.X	XX.X, XX.X	XX.X, XX.X	XX.X, XX.X
Time from surgery to first chemotherapy, days					
n	XXX	XXX	XXX	XXX	XXX
Mean (SD)	XX.X (XX.X)	XX.X (XX.X)	XX.X (XX.X)	XX.X (XX.X)	XX.X (XX.X)
Median (IQR)	XX.X (XX.X)	XX.X (XX.X)	XX.X (XX.X)	XX.X (XX.X)	XX.X (XX.X)
Min, Max	XX.X, XX.X	XX.X, XX.X	XX.X, XX.X	XX.X, XX.X	XX.X, XX.X
Time from last chemotherapy to randomisation, days					
n	XXX	XXX	XXX	XXX	XXX
Mean (SD)	XX.X (XX.X)	XX.X (XX.X)	XX.X (XX.X)	XX.X (XX.X)	XX.X (XX.X)
Median (IQR)	XX.X (XX.X)	XX.X (XX.X)	XX.X (XX.X)	XX.X (XX.X)	XX.X (XX.X)
Min, Max	XX.X, XX.X	XX.X, XX.X	XX.X, XX.X	XX.X, XX.X	XX.X, XX.X

Duration of chemotherapy, n (%)				
<3 months	XXX (XX.X)	XXX (XX.X)	XXX (XX.X)	XXX (XX.X)
3-6 months	XXX (XX.X)	XXX (XX.X)	XXX (XX.X)	XXX (XX.X)
>6 months	XXX (XX.X)	XXX (XX.X)	XXX (XX.X)	XXX (XX.X)
RT regimen (for rectal cancer only), n (%)*				
Neoadjuvant chemo RT	XXX (XX.X)	XXX (XX.X)	XXX (XX.X)	XXX (XX.X)
Tumour regression grade:				
Grade 1	XXX (XX.X)	XXX (XX.X)	XXX (XX.X)	XXX (XX.X)
Grade 2	XXX (XX.X)	XXX (XX.X)	XXX (XX.X)	XXX (XX.X)
Grade 3	XXX (XX.X)	XXX (XX.X)	XXX (XX.X)	XXX (XX.X)
Grade 4	XXX (XX.X)	XXX (XX.X)	XXX (XX.X)	XXX (XX.X)
Grade 5	XXX (XX.X)	XXX (XX.X)	XXX (XX.X)	XXX (XX.X)
Unknown	XXX (XX.X)	XXX (XX.X)	XXX (XX.X)	XXX (XX.X)
Neoadjuvant RT	XXX (XX.X)	XXX (XX.X)	XXX (XX.X)	XXX (XX.X)
Adjuvant RT	XXX (XX.X)	XXX (XX.X)	XXX (XX.X)	XXX (XX.X)
Adjuvant chemo RT	XXX (XX.X)	XXX (XX.X)	XXX (XX.X)	XXX (XX.X)
No RT	XXX (XX.X)	XXX (XX.X)	XXX (XX.X)	XXX (XX.X)
Time from first RT to randomisation, days				
n	XXX	XXX	XXX	XXX
Mean (SD)	XX.X (XX.X)	XX.X (XX.X)	XX.X (XX.X)	XX.X (XX.X)
Median (IQR)	XX.X (XX.X)	XX.X (XX.X)	XX.X (XX.X)	XX.X (XX.X)
Min, Max	XX.X, XX.X	XX.X, XX.X	XX.X, XX.X	XX.X, XX.X
Dose of RT (for rectal cancer only), Gy				
n	XXX	XXX	XXX	XXX

Mean (SD)	XX.X (XX.X)	XX.X (XX.X)	XX.X (XX.X)	XX.X (XX.X)	XX.X (XX.X)
Median (IQR)	XX.X (XX.X)	XX.X (XX.X)	XX.X (XX.X)	XX.X (XX.X)	XX.X (XX.X)
Min, Max	XX.X, XX.X	XX.X, XX.X	XX.X, XX.X	XX.X, XX.X	XX.X, XX.X
No. of fractions (for rectal cancer only)					
n	XXX	XXX	XXX	XXX	XXX
Mean (SD)	XX.X (XX.X)	XX.X (XX.X)	XX.X (XX.X)	XX.X (XX.X)	XX.X (XX.X)
Median (IQR)	XX.X (XX.X)	XX.X (XX.X)	XX.X (XX.X)	XX.X (XX.X)	XX.X (XX.X)
Min, Max	XX.X, XX.X	XX.X, XX.X	XX.X, XX.X	XX.X, XX.X	XX.X, XX.X

n: number of subjects; %: percentage of respective population pool treatment group; SD: standard deviation; IQR: interquartile range; RT: radiotherapy.
*Percentage of total rectal cancer subjects.

Table 4: Risk factors

	Modified intention-to-treat		Per-protocol	
	Aspirin (N=xxxx)	Placebo (N=xxxx)	Aspirin (N=xxxx)	Placebo (N=xxxx)
Tumour grade, n (%)				
Grade 1	xxx (xx.x)	xxx (xx.x)	xxx (xx.x)	xxx (xx.x)
Grade 2	xxx (xx.x)	xxx (xx.x)	xxx (xx.x)	xxx (xx.x)
Grade 3/4	xxx (xx.x)	xxx (xx.x)	xxx (xx.x)	xxx (xx.x)
Unknown	xxx (xx.x)	xxx (xx.x)	xxx (xx.x)	xxx (xx.x)
Lymphatic invasion, n (%)				
Yes	xxx (xx.x)	xxx (xx.x)	xxx (xx.x)	xxx (xx.x)
No	xxx (xx.x)	xxx (xx.x)	xxx (xx.x)	xxx (xx.x)
Unknown	xxx (xx.x)	xxx (xx.x)	xxx (xx.x)	xxx (xx.x)
Vascular invasion, n (%)				
Yes	xxx (xx.x)	xxx (xx.x)	xxx (xx.x)	xxx (xx.x)
No	xxx (xx.x)	xxx (xx.x)	xxx (xx.x)	xxx (xx.x)
Unknown	xxx (xx.x)	xxx (xx.x)	xxx (xx.x)	xxx (xx.x)
Perineural invasion, n (%)				
Yes	xxx (xx.x)	xxx (xx.x)	xxx (xx.x)	xxx (xx.x)
No	xxx (xx.x)	xxx (xx.x)	xxx (xx.x)	xxx (xx.x)
Unknown	xxx (xx.x)	xxx (xx.x)	xxx (xx.x)	xxx (xx.x)
Bowel obstruction, n (%)				
Yes	xxx (xx.x)	xxx (xx.x)	xxx (xx.x)	xxx (xx.x)

No	xxx (xx.x)	xxx (xx.x)	xxx (xx.x)	xxx (xx.x)
Unknown	xxx (xx.x)	xxx (xx.x)	xxx (xx.x)	xxx (xx.x)
Perforation, n (%)				
Yes	xxx (xx.x)	xxx (xx.x)	xxx (xx.x)	xxx (xx.x)
No	xxx (xx.x)	xxx (xx.x)	xxx (xx.x)	xxx (xx.x)
Unknown	xxx (xx.x)	xxx (xx.x)	xxx (xx.x)	xxx (xx.x)
Apical lymph nodes involved, n (%)				
Yes	xxx (xx.x)	xxx (xx.x)	xxx (xx.x)	xxx (xx.x)
No	xxx (xx.x)	xxx (xx.x)	xxx (xx.x)	xxx (xx.x)
Unknown	xxx (xx.x)	xxx (xx.x)	xxx (xx.x)	xxx (xx.x)
Alcohol history, n (%)				
No	xxx (xx.x)	xxx (xx.x)	xxx (xx.x)	xxx (xx.x)
Current social drinker	xxx (xx.x)	xxx (xx.x)	xxx (xx.x)	xxx (xx.x)
Current habitual drinker	xxx (xx.x)	xxx (xx.x)	xxx (xx.x)	xxx (xx.x)
Ex-drinker	xxx (xx.x)	xxx (xx.x)	xxx (xx.x)	xxx (xx.x)
Smoking history, n (%)				
No	xxx (xx.x)	xxx (xx.x)	xxx (xx.x)	xxx (xx.x)
Yes	xxx (xx.x)	xxx (xx.x)	xxx (xx.x)	xxx (xx.x)
Number of years smoking, mean (SD)	xx.x (xx.x)	xx.x (xx.x)	xx.x (xx.x)	xx.x (xx.x)

n: number of subjects; %: percentage of respective population pool treatment group; SD: standard deviation.

Table 5: Medical history, family history, and vital signs

	Modified intention-to-treat		Per-protocol	
	Aspirin (N=xxxx)	Placebo (N=xxxx)	Aspirin (N=xxxx)	Placebo (N=xxxx)
Medical history				
Asthma, n (%)				
Current active	xxx (xx.x)	xxx (xx.x)	xxx (xx.x)	xxx (xx.x)
Past history	xxx (xx.x)	xxx (xx.x)	xxx (xx.x)	xxx (xx.x)
No	xxx (xx.x)	xxx (xx.x)	xxx (xx.x)	xxx (xx.x)
Unknown	xxx (xx.x)	xxx (xx.x)	xxx (xx.x)	xxx (xx.x)
Diabetes, n (%)				
Current active	xxx (xx.x)	xxx (xx.x)	xxx (xx.x)	xxx (xx.x)
Past history	xxx (xx.x)	xxx (xx.x)	xxx (xx.x)	xxx (xx.x)
No	xxx (xx.x)	xxx (xx.x)	xxx (xx.x)	xxx (xx.x)
Unknown	xxx (xx.x)	xxx (xx.x)	xxx (xx.x)	xxx (xx.x)
Coronary arterial disease, n (%)				
Current active	xxx (xx.x)	xxx (xx.x)	xxx (xx.x)	xxx (xx.x)
Past history	xxx (xx.x)	xxx (xx.x)	xxx (xx.x)	xxx (xx.x)
No	xxx (xx.x)	xxx (xx.x)	xxx (xx.x)	xxx (xx.x)
Unknown	xxx (xx.x)	xxx (xx.x)	xxx (xx.x)	xxx (xx.x)
Angina, n (%)				
Current active	xxx (xx.x)	xxx (xx.x)	xxx (xx.x)	xxx (xx.x)
Past history	xxx (xx.x)	xxx (xx.x)	xxx (xx.x)	xxx (xx.x)
No	xxx (xx.x)	xxx (xx.x)	xxx (xx.x)	xxx (xx.x)

Unknown	xxx (xx.x)	xxx (xx.x)	xxx (xx.x)	xxx (xx.x)
Vascular disease, n (%)				
Current active	xxx (xx.x)	xxx (xx.x)	xxx (xx.x)	xxx (xx.x)
Past history	xxx (xx.x)	xxx (xx.x)	xxx (xx.x)	xxx (xx.x)
No	xxx (xx.x)	xxx (xx.x)	xxx (xx.x)	xxx (xx.x)
Unknown	xxx (xx.x)	xxx (xx.x)	xxx (xx.x)	xxx (xx.x)
Stroke, n (%)				
Current active	xxx (xx.x)	xxx (xx.x)	xxx (xx.x)	xxx (xx.x)
Past history	xxx (xx.x)	xxx (xx.x)	xxx (xx.x)	xxx (xx.x)
No	xxx (xx.x)	xxx (xx.x)	xxx (xx.x)	xxx (xx.x)
Unknown	xxx (xx.x)	xxx (xx.x)	xxx (xx.x)	xxx (xx.x)
Gastrointestinal ulcer, n (%)				
Current active	xxx (xx.x)	xxx (xx.x)	xxx (xx.x)	xxx (xx.x)
Past history	xxx (xx.x)	xxx (xx.x)	xxx (xx.x)	xxx (xx.x)
No	xxx (xx.x)	xxx (xx.x)	xxx (xx.x)	xxx (xx.x)
Unknown	xxx (xx.x)	xxx (xx.x)	xxx (xx.x)	xxx (xx.x)
Gastrointestinal bleeding, n (%)				
Current active	xxx (xx.x)	xxx (xx.x)	xxx (xx.x)	xxx (xx.x)
Past history	xxx (xx.x)	xxx (xx.x)	xxx (xx.x)	xxx (xx.x)
No	xxx (xx.x)	xxx (xx.x)	xxx (xx.x)	xxx (xx.x)
Unknown	xxx (xx.x)	xxx (xx.x)	xxx (xx.x)	xxx (xx.x)
Other cancers, n (%)				

Current active	xxx (xx.x)	xxx (xx.x)	xxx (xx.x)	xxx (xx.x)
Past history	xxx (xx.x)	xxx (xx.x)	xxx (xx.x)	xxx (xx.x)
No	xxx (xx.x)	xxx (xx.x)	xxx (xx.x)	xxx (xx.x)
Unknown	xxx (xx.x)	xxx (xx.x)	xxx (xx.x)	xxx (xx.x)
ECOG at screening, n (%)				
0: Asymptomatic	xxx (xx.x)	xxx (xx.x)	xxx (xx.x)	xxx (xx.x)
1: Symptomatic but completely ambulatory	xxx (xx.x)	xxx (xx.x)	xxx (xx.x)	xxx (xx.x)
2: <50% in bed during the day	xxx (xx.x)	xxx (xx.x)	xxx (xx.x)	xxx (xx.x)
3: >50% in bed, but not bedbound	xxx (xx.x)	xxx (xx.x)	xxx (xx.x)	xxx (xx.x)
4: Bedbound	xxx (xx.x)	xxx (xx.x)	xxx (xx.x)	xxx (xx.x)
Family history				
Number of family members with colorectal cancer (1 st and 2 nd degree relatives only), n (%)				
Nil	xxx (xx.x)	xxx (xx.x)	xxx (xx.x)	xxx (xx.x)
One	xxx (xx.x)	xxx (xx.x)	xxx (xx.x)	xxx (xx.x)
Two	xxx (xx.x)	xxx (xx.x)	xxx (xx.x)	xxx (xx.x)
Three	xxx (xx.x)	xxx (xx.x)	xxx (xx.x)	xxx (xx.x)
≥ Four	xxx (xx.x)	xxx (xx.x)	xxx (xx.x)	xxx (xx.x)
Vital signs at screening				
Weight, kg				
n	xxx	xxx	xxx	xxx
Mean (SD)	xx.x (xx.x)	xx.x (xx.x)	xx.x (xx.x)	xx.x (xx.x)
Median (IQR)	xx.x (xx.x)	xx.x (xx.x)	xx.x (xx.x)	xx.x (xx.x)
Min, Max	xx.x, xx.x	xx.x, xx.x	xx.x, xx.x	xx.x, xx.x

Height, cm					
n	XXX	XXX	XXX	XXX	XXX
Mean (SD)	XX.X (XX.X)	XX.X (XX.X)	XX.X (XX.X)	XX.X (XX.X)	XX.X (XX.X)
Median (IQR)	XX.X (XX.X)	XX.X (XX.X)	XX.X (XX.X)	XX.X (XX.X)	XX.X (XX.X)
Min, Max	XX.X, XX.X	XX.X, XX.X	XX.X, XX.X	XX.X, XX.X	XX.X, XX.X
Systolic blood pressure, mmHg					
n	XXX	XXX	XXX	XXX	XXX
Mean (SD)	XX.X (XX.X)	XX.X (XX.X)	XX.X (XX.X)	XX.X (XX.X)	XX.X (XX.X)
Median (IQR)	XX.X (XX.X)	XX.X (XX.X)	XX.X (XX.X)	XX.X (XX.X)	XX.X (XX.X)
Min, Max	XX.X, XX.X	XX.X, XX.X	XX.X, XX.X	XX.X, XX.X	XX.X, XX.X
Diastolic blood pressure, mmHg					
n	XXX	XXX	XXX	XXX	XXX
Mean (SD)	XX.X (XX.X)	XX.X (XX.X)	XX.X (XX.X)	XX.X (XX.X)	XX.X (XX.X)
Median (IQR)	XX.X (XX.X)	XX.X (XX.X)	XX.X (XX.X)	XX.X (XX.X)	XX.X (XX.X)
Min, Max	XX.X, XX.X	XX.X, XX.X	XX.X, XX.X	XX.X, XX.X	XX.X, XX.X

n: number of subjects; %: percentage of respective population pool treatment group; SD: standard deviation; IQR: interquartile range.

Table 6: Laboratory investigations at screening

	Modified intention-to-treat		Per-protocol	
	Aspirin (N=xxxx)	Placebo (N=xxxx)	Aspirin (N=xxxx)	Placebo (N=xxxx)
Haematology				
Haemoglobin, g/dL				
n	xxx	xxx	xxx	xxx
Mean (SD)	xx.x (xx.x)	xx.x (xx.x)	xx.x (xx.x)	xx.x (xx.x)
Median (IQR)	xx.x (xx.x)	xx.x (xx.x)	xx.x (xx.x)	xx.x (xx.x)
Min, Max	xx.x, xx.x	xx.x, xx.x	xx.x, xx.x	xx.x, xx.x
Clinically significant, n (%)	xx (xx.x)	xx (xx.x)	xx (xx.x)	xx (xx.x)
Platelet count, 10⁹/L				
n	xxx	xxx	xxx	xxx
Mean (SD)	xx.x (xx.x)	xx.x (xx.x)	xx.x (xx.x)	xx.x (xx.x)
Median (IQR)	xx.x (xx.x)	xx.x (xx.x)	xx.x (xx.x)	xx.x (xx.x)
Min, Max	xx.x, xx.x	xx.x, xx.x	xx.x, xx.x	xx.x, xx.x
Clinically significant, n (%)	xx (xx.x)	xx (xx.x)	xx (xx.x)	xx (xx.x)
Biochemistry				
Creatinine, µmol/L				
n	xxx	xxx	xxx	xxx
Mean (SD)	xx.x (xx.x)	xx.x (xx.x)	xx.x (xx.x)	xx.x (xx.x)
Median (IQR)	xx.x (xx.x)	xx.x (xx.x)	xx.x (xx.x)	xx.x (xx.x)
Min, Max	xx.x, xx.x	xx.x, xx.x	xx.x, xx.x	xx.x, xx.x
Clinically significant, n (%)	xx (xx.x)	xx (xx.x)	xx (xx.x)	xx (xx.x)

Serum bilirubin, $\mu\text{mol/L}$
 
n
 
Mean (SD)
 
Median (IQR)
 
Min, Max
 
Clinically significant, n (%)
	
XXX
 
XX.X (XX.X)
 
XX.X (XX.X)
 
XX.X, XX.X
 
XX (XX.X)
	
XXX
 
XX.X (XX.X)
 
XX.X (XX.X)
 
XX.X, XX.X
 
XX (XX.X)
	
XXX
 
XX.X (XX.X)
 
XX.X (XX.X)
 
XX.X, XX.X
 
XX (XX.X)
	
XXX
 
XX.X (XX.X)
 
XX.X (XX.X)
 
XX.X, XX.X
 
XX (XX.X)

AST, μL
 
n
 
Mean (SD)
 
Median (IQR)
 
Min, Max
 
Clinically significant, n (%)
	
XXX
 
XX.X (XX.X)
 
XX.X (XX.X)
 
XX.X, XX.X
 
XX (XX.X)
	
XXX
 
XX.X (XX.X)
 
XX.X (XX.X)
 
XX.X, XX.X
 
XX (XX.X)
	
XXX
 
XX.X (XX.X)
 
XX.X (XX.X)
 
XX.X, XX.X
 
XX (XX.X)
	
XXX
 
XX.X (XX.X)
 
XX.X (XX.X)
 
XX.X, XX.X
 
XX (XX.X)

ALT, μL
 
n
 
Mean (SD)
 
Median (IQR)
 
Min, Max
 
Clinically significant, n (%)
	
XXX
 
XX.X (XX.X)
 
XX.X (XX.X)
 
XX.X, XX.X
 
XX (XX.X)
	
XXX
 
XX.X (XX.X)
 
XX.X (XX.X)
 
XX.X, XX.X
 
XX (XX.X)
	
XXX
 
XX.X (XX.X)
 
XX.X (XX.X)
 
XX.X, XX.X
 
XX (XX.X)
	
XXX
 
XX.X (XX.X)
 
XX.X (XX.X)
 
XX.X, XX.X
 
XX (XX.X)

